**PE37: A multicenter randomized trial of screening with sFlt1/PIGF and selective labor induction to prevent preeclampsia at term.**

Primary Site:
 
BCNatal (Hospital Clínic and Hospital Sant Joan de Déu) and Hospital Sant Pau, Barcelona, Spain

Principal Investigators:
 
[name], [name] and [name]

Disease Studied and Intervention
 
Preeclampsia in late pregnancy

Cohort:
 
Non-selected nulliparous pregnant women routinely attended at 35-36 weeks' gestation and randomized to revealed versus concealed maternal angiogenic factors levels.

Inclusion and Exclusion Criteria:
 
Inclusion criteria:
 
 
1. Nulliparous women
 
2. Singleton pregnancies
 
3. >18 years old
 
4. 35.0-36.6 weeks of gestation
 
5. Maternal written consent form
 
6. Planned vaginal delivery
 
 
Exclusion criteria:
 
-Any maternal or fetal complications that require labor induction before 38 weeks according to local institutional protocols (including established preeclampsia).

Study Type
 
Prospective, open-label randomized multicentre study with parallel groups conducted at BCNatal (Hospital Clínic and Hospital Sant Joan de Deu) (Barcelona), Hospital Sant Pau (Barcelona), Hospital la Paz (Madrid), Hospital del Mar (Barcelona), Hospital la Fe (Valencia), Hospital Son Llatzer (Mallorca), Hospital Can Ruti (Badalona), Hospital Clínico de Zaragoza, Hospital Arrixaca de Murcia and Complejo Hospitalario Universitario Insular Materno Infantil (Las Palmas de Gran Canaria) (Spain), Institute for the Care of Mother and Child, Prague, Prague, Czechia, Centre of Postgraduate Medical Education, Obstetrics and Gynecology and Perinatal Medicine, Warsaw, Poland;

Gynecology and Obstetrics - CHU Liège; Belgium.

Intervention
 
 
Revealed arm: Blood sampling at 35+0-36+6w to determine sFlt-1/PlGF ratio. The result will be known by managing clinicians and, if >90th centile, labour induction from 37+0 weeks will be offered.
 
Concealed arm: The result of sFlt1/PlGF ratio will be unknown. Routine follow-up
 

Duration
 
3 years

Date Of First Enrolment
 
February 2021

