### Objectives

To evaluate the impact of a policy of induction of labour from 37 weeks of gestation in nulliparous women at risk for preeclampsia as defined by a sFlt1/PIGF ratio >90th centile at 35-36 weeks of gestation on the prevalence of term PE.

As secondary objectives, the study will evaluate the impact of the sFlt1/PIGF screening on:

1. Cesarean section rates
2. Perinatal morbidity
3. Maternal pregnancy-related morbidity.
4. Maternal post-pregnancy endothelial function.
5. Cost-efficiency analysis (hospital maternal and neonatal stay and incurred costs).
6. Maternal experience.

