#### Inclusion and Exclusion Criteria:

Inclusion criteria:

- Nulliparous women

PE37 Trial 19 Feb 2021 Version 7.0

- Singleton pregnancies
- >18 years old
- 35.0-36.6 weeks of gestation
- Maternal written consent form
- Planned vaginal delivery

Exclusion criteria:

- Any maternal or fetal complications that require labor induction before 38 weeks according to local institutional protocols (including established preeclampsia).

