**Outcome variables**

Main outcome variables: development of term preeclampsia.

Secondary outcome variables:

- Caesarean section rate
- Incidence of perinatal complications defined as the presence of placental abruption, severe fetal growth restriction (defined as birth weight <3rd centile), perinatal mortality, an Apgar score at 5-minute below 7.0, an umbilical artery pH below 7.10, need for respiratory support within 72 hours after birth neonatal intraventricular haemorrhage grade III/IV, necrotizing enterocolitis, periventricular leukomalacia, sepsis, bronchopulmonary dysplasia or hypoxic ischemic encephalopathy.
- Incidence of maternal complications, defined by a composite including any of the following: (i) HELLP syndrome (lactate dehydrogenase [LDH] >700 IU/L, AST to twice normal values and platelet count <100x10^9/L); (ii) Central nervous system dysfunction (eclampsia, Glasgow Coma Score <13 (12), stroke, reversible ischemic neurological deficit or cortical blindness); (iii) hepatic dysfunction (INR >1.2 in the absence of disseminated intravascular coagulation, MELD score >10 (16), or hepatic hematoma or rupture); (iv) renal dysfunction (dialysis, serum creatinine concentration greater than 150 µmol/L, or urine output <0.5 mL/kg/h during 12 hours, according to renal insufficiency by RIFLE criteria; or need for treatment with furosemide to maintain urine output >0.5 mL/kg/h for 3 hours); (v) respiratory dysfunction (pulmonary edema, requirement of invasive or non-invasive mechanical ventilation, oxygen requirement greater than 50% concentration for longer than 1 hour, or severe breathing difficulty [no criteria of pulmonary edema but presence of dyspnea, crackles in pulmonary auscultation, and SaO2<90%]); (vi) cardiovascular dysfunction (need for inotropic support, left ventricle failure, or myocardial infarction); (vii) placental abruption; or, (viii) a requirement for transfusion of blood products.
- Maternal blood pressure and endothelial function 6-months postpartum.
- Maternal and neonatal hospital stay duration (days).
- Maternal satisfaction and experience assessed by questionnaires (PSS, STAI, WHO and Labor Agency scale).

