**Sample size calculation**

8302 nulliparous women are planned to be include demonstrating a 50% reduction of development of PE (from 1.5%). Assuming a 10% loss, the investigators estimated a sample size of 9132 women.

*R Syntax:*

```
library(SampleSize4ClinicalTrials)

ssc_propcomp (1L,ratio=1,alpha=0.05,power=0.9,p1=0.0075, p2=0.015)
```

Under a non-inferiority hypothesis testing design, assuming a composite adverse neonatal outcome incidence of 1% in the revealed group, 0.5% in the concealed risk and a prespecified non-inferiority margin of 0.25%; this sample size (4151 per arm) would result in a power of 99% to reject the null hypothesis that the reveal strategy increases the neonatal complications.

*R Syntax:*

```
library(SampleSize4ClinicalTrials)

ssc_propcomp (3L,ratio=1,alpha=0.05,power=0.99,p1=0.005, p2=0.01, delta=0.0025)
```

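### A term-only primary outcome leaves PE between randomisation and 37+0 uncounted, possibly unequally by arm, and disagrees with the outcome used for the sample size

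*Protocol*

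**What the plan says.** The Outcome variables section of the protocol states "Main outcome variables: development of term preeclampsia". The Objectives section likewise speaks of the effect of the policy "on the prevalence of term PE". Neither says whether *term* refers to the date of diagnosis or the date of delivery.

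The Sample size calculation section, and the matching row of the synopsis, use a different outcome. The trial is sized for "demonstrating a 50% reduction of development of PE (from 1.5"%), with no restriction to term.

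Women are eligible at "35.0-36.6 weeks of gestation". The synopsis describes the revealed arm as "Blood sampling at 35+0-36+6w to determine sFlt-1/PlGF ratio", and adds that "The result will be known by managing clinicians". The one stated response to a ratio above the 90th centile is that "labour induction from 37+0 weeks will be offered". In the concealed arm the ratio is unknown and follow-up is routine.

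Four other statements bear on the point. The exclusion criterion removes PE already established at enrolment, not PE that arises later. The Randomization section says that neither women nor obstetric staff can be blinded. The Statistical analysis section specifies intention to treat. The Background section on angiogenic factors says that the ratio is now accepted in diagnosing PE when the disease is suspected.

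**The concern.** The clock starts 14 days to 1 day before 37+0, but a literal reading of the primary outcome starts counting only at 37+0. PE in between is a post-randomisation event with no stated place in the primary count. Intention to treat does not repair this, because it keeps the woman in the denominator and does not restore her event to the numerator.

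If the two arms lost the same number of cases this way, the term-PE comparison would be incomplete but not biased. The difficulty is that the arms hold different information during that interval. Revealed-arm clinicians know the ratio, which the protocol itself treats as diagnostically useful, and concealed-arm clinicians do not. If that knowledge brought some diagnoses forward across 37+0, revealed-arm cases would leave the endpoint without any having been prevented. The trial could then report less term PE without showing less PE.

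The two outcome wordings also leave open whether the planned 1.5% means term PE or all PE after randomisation. That determines what a change of endpoint would cost.

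**Working it through.** **Inputs.** From Sample size calculation: 0.75% versus 1.5%, alpha 0.05, power 0.90, 1:1 allocation. From Table 1, at a 10% screen-positive rate: detection rate 82% and PPV 3.8% for delivery with PE within 2 weeks; 62% and 8.8% within 4 weeks. From the synopsis: sampling at 35+0 to 36+6.

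**Assumptions.** Table 1 applies to the trial population; sampling days are spread evenly; the rate of PE is constant within each two-week period; any advance in diagnosis is 3, 5 or 7 days. The protocol gives no figure for the last.

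**1. The plan's own figure.** Two proportions, unpooled variance, two-sided: n = [0.0075 × 0.9925 + 0.015 × 0.985] × (1.960 + 1.282)² / 0.0075² = 4150.4. This gives 4151 per arm and 8302 in total, as stated. Expected events are 4151 × 0.015 = 62 (concealed) and 4151 × 0.0075 = 31 (revealed).

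**2. Incidence implied by Table 1** (screen-positive rate × PPV / detection rate).
- Within 2 weeks: 0.10 × 3.8% / 0.82 = 0.46%.
- Within 4 weeks: 0.10 × 8.8% / 0.62 = 1.42%. This is close to the planned 1.5% and is not restricted to term.

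**3. PE between sampling and 37+0.** The mean interval is (1 + 2 + … + 14)/14 = 7.5 days. Then 0.463% × 7.5/14 = 0.248%, and 0.00248 × 4151 = 10.3 women per arm, of whom 0.82 × 10.3 = 8.5 are screen-positive. If every woman were sampled at 35+0, the figure would be 0.463% × 4151 = 19 per arm. If the rate rises linearly to fit both Table 1 incidences, it is about 8.6 per arm.

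**4. Cases that an earlier diagnosis could move.** Among all women, screen-positive cases arise at 0.10 × 3.8% = 0.38% over the first 14 days after sampling (0.0271% per day) and at 0.88% − 0.38% = 0.50% over the next 14 (0.0357% per day). Averaging over sampling 1 to 14 days before 37+0, the k days after 37+0 split between those two periods as follows.

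| k (days) | days in first / second period | rate | cases of 4151 | share of 1.5% |
|---|---|---|---|---|
| 3 | 2.571 / 0.429 | 0.085% | 3.5 | 5.7% |
| 5 | 3.929 / 1.071 | 0.145% | 6.0 | 9.7% |
| 7 | 5 / 2 | 0.207% | 8.6 | 13.8% |

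These are ceilings. They assume that *term* means diagnosed at or after 37+0, that the result is available at once (turnaround is not stated), and that induction would have averted none of the cases.

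**5. Effect on the test.** With no true prevention, moving 4 cases out of the revealed arm gives a risk ratio of 0.94 and a 5.6% chance of a significant benefit; moving 8 gives 0.87 and 11%. The nominal figure is 2.5%. Producing the whole planned halving would need about 31 cases.

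**6. Cost of making total PE primary.** If 1.5% already means all PE after randomisation, N stays at 8302. If it means term PE only, adding 0.25 points to both arms with the absolute difference kept gives 1.75% versus 1.00%: power at 4151 per arm is 83.5%, and 90% power would need 10124 women. With 0.46 points added, power is 78%.

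**The case against.** The strongest reply is that the mechanism is not in the protocol. The only planned action on a high ratio takes effect from 37+0. No additional visits or tests before then are described, and the Randomization section says that obstetric management will follow similar protocols in the centres. This stands: differential early diagnosis is a risk, not a documented feature, and the 3 to 7 days are assumed.

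Second, *term* is not defined and the protocol uses it loosely. The section on prediction and prevention speaks of term PE within 2 and 4 weeks of a test at 35 to 36 weeks, which would include cases before 37+0. If *term* means delivered at or after 37+0, a woman diagnosed earlier but delivered at term still counts, and the loss shrinks to preterm deliveries. This also stands, but it leaves the primary numerator undetermined rather than settled.

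Third, closer attention to screen-positive women might uncover mild PE that routine care would miss, which would count against the intervention. That is possible for diagnoses from 37+0 onward. Earlier extra diagnoses would themselves be dropped under a term-by-diagnosis rule, so they would not offset the loss.

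Fourth, the women concerned are those offered induction from 37+0. A case that induction would have averted was never going to enter the term count, so diagnosing it earlier does not alter that count.

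Fifth, supporting analyses are commonly left to the SAP, which is not shown. That answers a complaint about missing detail. It does not answer the disagreement within the protocol over what the primary outcome is.

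**Conclusion.** The point holds as a weakness in how the primary outcome is fixed. The objective and outcome sections say term PE, the sample size says PE, and a literal term-only count drops about 0.25% of women, roughly 10 per arm (8.6 to 19 under the alternative assumptions), with a possible imbalance by arm. The imbalance could create at most a spurious 6% to 14% relative reduction if diagnosis came forward by 3 to 7 days. It would be smaller if *term* refers to delivery or if induction would have averted the cases.

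A reader might infer that the protocol builds in a bias favouring the intervention, so that a positive result would merely reflect earlier diagnosis. The documents do not support that. They plan no extra checks before 37+0, they do not tie *term* to diagnosis, the direction is not fixed, and 3.5 to 8.6 cases fall well short of the 31 needed for the planned effect. What can be said is that the endpoint is open to this distortion, that intention to treat does not remove it, and that closing the gap is cheap. The change should be made.

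**What to change.** 1. Reconcile the outcome wording in Objectives and Outcome variables with that in Sample size calculation and the synopsis, and state which of the two the 1.5% refers to.
2. Define *term* by date of diagnosis or date of delivery.
3. Pre-specify all PE from randomisation to the end of the 6-week puerperium, at any gestation and by allocated arm, as a required key analysis beside term PE. Report PE before 37+0 by arm.
4. Claim that the strategy prevents PE only if total PE is also lower in the revealed arm.

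If 1.5% was meant as all PE after randomisation, total PE can be the primary outcome with no change in N. If it was meant as term PE only, making total PE primary would lower power from 90% to about 84%, because it adds cases that induction from 37+0 cannot prevent. Total PE is then better kept as the key supporting analysis, which needs no extra women.

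The practical cost is in data capture. Data collection and analysis says that outcome data are abstracted from records but does not name the date of PE diagnosis, so that field must be confirmed or added.

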### **IOL at 37 weeks as an intervention in women at high-risk for PE.**

Previous trials based on statins have failed to show a reduction of PE in high-risk women. IOL at 37 weeks is an alternative to avoid PE in those high-risk women. IOL has consistently been demonstrated to be safe (13) and does not affect long-term maternal quality of life (14). Both the HYPITAT and the DIGITAT randomized trials showed that IOL did not increase

caesarean rates or adverse neonatal outcomes (15). A recent large randomized trial in the US has shown that even in low-risk women, universal IOL decreased cesarean section rates and was well accepted (16). While in low-risk pregnancies labour induction has been found to be beneficial from 39 weeks (ARRIVE study), in women with placental-related conditions such as hypertension (HYPITAT) or small-for-gestational age (DIGITAT) it is 37+ weeks when the trade-off between neonatal and maternal benefits makes induction recommendable.

Therefore, the investigators hypothesize that a single-step universal screening for term PE based on sFlt1/PIGF ratio at 35-36.6 w followed by IOL at 37w in those women found to be at high risk might represent a feasible and reproducible strategy, applicable worldwide, to reduce the prevalence of term PE without increasing cesarean section rates or adverse neonatal outcomes.

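### The 99% non-inferiority power rests on a neonatal composite that is not identified, on rates that fit the only defined composite poorly, and on arms reversed between text and code

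*Protocol*

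**What the plan says.** The protocol's hypothesis is that screening followed by induction will reduce term preeclampsia "without increasing cesarean section rates or adverse neonatal outcomes" (section on induction at 37 weeks; the executive summary says much the same).

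Under Sample size calculation, the neonatal part is planned as a non-inferiority comparison, "assuming a composite adverse neonatal outcome incidence of 1% in the revealed group, 0.5% in the concealed risk", with "a prespecified non-inferiority margin of 0.25" per cent. It concludes that "this sample size (4151 per arm) would result in a power of 99" per cent "to reject the null hypothesis that the reveal strategy increases the neonatal complications". The R call given for this is "ssc_propcomp (3L,ratio=1,alpha=0.05,power=0.99,p1=0.005, p2=0.01, delta=0.0025"). The components of the composite are not listed there.

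Under Outcome variables, two composites are defined. One is maternal. The other is called perinatal complications. It counts placental abruption, "severe fetal growth restriction (defined as birth weight <3rd centile"), perinatal death, 5-minute Apgar below 7, cord pH below 7.10, respiratory support in the first 72 hours, sepsis and several rarer neonatal diagnoses. No expected incidence and no birth-weight reference is given.

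**The concern.** The planning rates and the outcome definition do not fit together. Birth weight below the 3rd centile is nominally about 3% in a reference population. With the other components added, a total of 0.5% in one arm and 1% in the other looks too low for the only composite that could be meant. At a fixed absolute margin, a higher event rate means a larger standard error and less power.

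The text also gives the revealed arm the higher rate. That puts the assumed true difference (0.5 points) beyond the margin (0.25 points), so a power of 99% cannot follow from the rates as written.

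Neonatal safety is part of the trial's hypothesis. If the stated power is not real, an inconclusive neonatal result becomes likely even when induction does no harm, and readers of the protocol have been told otherwise.

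**Working it through.** **Inputs (Sample size calculation).** n = 4151 per arm; margin 0.0025; rates 0.5% and 1%; alpha 0.05, sidedness not stated. The 4151 comes from the primary endpoint, "ssc_propcomp (1L,ratio=1,alpha=0.05,power=0.9,p1=0.0075, p2=0.015"): unpooled and two-sided, (1.960 + 1.282)² × (0.0075×0.9925 + 0.015×0.985) / 0.0075² = 4150.4, rounded up to 4151. It is the number before the 10% allowance for loss.

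**Formula.** Power = Φ[(margin − (p_revealed − p_concealed)) / SE − z], with SE = √{[p_r(1−p_r) + p_c(1−p_c)] / 4151}. For a one-sided 5% test z = 1.645; for 2.5%, z = 1.960.

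**Step 1: reproduce the 99%.** SE = √(0.014875/4151) = 0.001893.
- Revealed 0.5%, concealed 1%: (0.0025 + 0.005)/0.001893 − 1.645 = 2.317, power 99.0%. The n for exactly 99% is 4171, close to 4151. At one-sided 2.5% the power is 97.7%.
- Revealed 1%, concealed 0.5%, as the text says: (0.0025 − 0.005)/0.001893 − 1.645 = −2.966, power 0.15%.

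So the 99% is the power when the revealed arm has half the events. This agrees with the order of arguments in the primary call, where p1 is the reduced rate expected with the intervention. It contradicts the sentence above the neonatal call.

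**Step 2: no true difference.** SE = √[2p(1−p)/4151]. For p = 3%, SE = 0.003744 and 0.0025/0.003744 − 1.645 = −0.977, power 16.4%.

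| True rate, both arms | One-sided 5% | One-sided 2.5% |
|---|---|---|
| 0.5% | 49% | 37% |
| 1% | 31% | 21% |
| 2% | 20% | 13% |
| 3% | 16% | 10% |
| 5% | 13% | 8% |
| 6% | 12% | 7% |

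Simulation at 3% gives 16.4% and 9.7%. For 90% power at one-sided 5%, the numbers per arm would be 13,634 at a 0.5% rate, 27,131 at 1% and 79,747 at 3%.

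**Step 3: change only the composite.** Add an independent 3% component to both arms and keep the half-point difference. The rates become 1 − 0.97×0.995 = 3.49% and 1 − 0.97×0.99 = 3.97%, with SE = 0.00416.
- Difference favouring revealed, as in the R call: (0.0025 + 0.00485)/0.00416 − 1.645 = 0.12, power about 55%.
- Difference against revealed, as in the text: power about 1.4%.

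With an added component of 1% instead of 3%, the favourable case gives 83%.

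**The case against.** Several points on the other side are sound.

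- **Cause.** A reader might infer that the birth-weight component alone brings power down from 99% to the 12% to 20% range. It does not. Most of the fall comes from dropping the assumed benefit: with equal arms, power is already 49% at 0.5% and 31% at 1% without that component. Adding 3% and keeping the benefit leaves about 55%.
- **The 3% figure.** A reader might take it as true by definition. No birth-weight reference is named, the women are nulliparous, and fetal complications requiring induction before 38 weeks are excluded, which may remove some of the smallest fetuses. It is an assumption, hence the 2% to 6% range. The 20% figure belongs to a 2% rate; from 3% upwards the range is 12% to 16%.
- **Dilution.** A reader might argue that events unrelated to induction hide a real harm. On an absolute margin this effect is negligible: an unrelated 3% component multiplies a difference by 0.97, so 0.50 points becomes 0.485. The chance of wrongly concluding non-inferiority at the margin moves from 5.0% to about 5.2%. What the component adds is variance.
- **Which composite.** The outcome section says perinatal and the power statement says neonatal. A narrower composite may be intended and may be defined in an analysis plan not shown here. If so, the defect is that the protocol quotes a power for an outcome it does not identify; the remedy is the same.
- **Weight.** This is a secondary outcome, and the trial was sized on the primary one.

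None of this rescues the 99%. It needs both the low rates and a halving of neonatal events under the revealed strategy, whereas the hypothesis claims only no increase.

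**Conclusion.** The concern holds in this form: the protocol states a power for a composite it does not identify, at rates that fit the only candidate poorly, with an assumed direction that differs between text and code. The rates as written give 0.15%. With no true difference, 4151 per arm and a one-sided 5% test, power is at most 49% within the protocol's own 0.5% to 1% range, and 12% to 20% if the defined composite occurs in 2% to 6% of births (7% to 13% at one-sided 2.5%). None of the scenarios that combine the defined composite with the 0.25-point margin comes near 99%; the more favourable ones, 55% and 83%, require induction to reduce neonatal events.

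The results rest on three assumptions: the 2% to 6% rate, the normal approximation with unpooled variance, and full data on 4151 per arm. The documents do not support the stronger conclusion that the birth-weight component must be removed. Taking it out would still leave 31% to 49% at rates of 0.5% to 1%, and the protocol itself treats small-for-gestational age as a placental condition, so keeping it is defensible.

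**What to change.** In the sample size section:

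1. State which composite the non-inferiority test uses, by reference to the outcome list or by listing its components.
2. Give assumed rates for that same composite and, if birth weight below the 3rd centile stays in, name the birth-weight reference.
3. Reconcile the direction of the assumed rates with the R call, and state whether alpha is one-sided 5% or 2.5%.
4. Replace the 99% with the power that 4151 per arm delivers at the 0.25-point margin under no true difference. If a benefit is to be assumed, say so, justify it, and show that power alongside.

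Reporting birth weight below the 3rd centile separately from the tested composite is optional; the reason would be the variance it adds.

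The cost is protocol wording and one recalculation, with no extra participants or data. The drawback is that the stated power becomes much less favourable, and the protocol would have to say that the neonatal comparison may well be inconclusive at this margin.
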